8.2 Blinding

Owing to study procedures, children, their parents and physicians will not be masked to the practices' random allocation.

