8.7 Trial assessments

Assessment by physician

During the first consultation at baseline, a selection of **clinical features** will be assessed and recorded by the physician in the patient's health record and on the e-CRF, **including the clinical decision tree** (clinician's gut feeling, body temperature, dypnoea). **CRP testing** will be conducted as per the **diagnostic algorithm** as described above (See Flowchart).

The physician will be asked to note in the patient's health record and on the e-CRF whether antibiotics were prescribed, whether this was an immediate or delayed prescription. If the decision to prescribe antibiotics diverted from the suggested algorithm in the intervention arm, physicians will be asked to acknowledge this and explain why on the e-CRF.

Any additional care during follow-up will be left at the discretion of the child's physician. We will use a **point-of-care CRP** test which requires 1.5 μ I of capillary blood obtained by finger prick (results within 4 minutes). Clinical features will be recorded before the CRP test is conducted.

Follow-up (app)

Follow-up information for all children will be collected using direct patient/parent contact using a smartphone app. Information regarding the smartphone app as well as instructions on how to install will be handed to children and their parents at the baseline consultation.

The smartphone app will ask parents and/or children about daily symptoms such as body temperature, cough, treatment and whether they consulted a physician or went to the hospital. The daily follow-up will consist of a maximum of 10 short questions which are answered by ticking the appropriate box. Parents will be asked to complete these questions once a day until the symptoms have resolved and the child is considered cured of the acute illness.

Furthermore, the app will ask parents to complete a few quality-of-life items (proxy version of the EQ-5D-Y questionnaire)(24) and two pain scales (Wong Baker FACES Pain Scale, FLACC scale)(25,26) during follow-up. Some items will be requested daily (visual analogue scale of the proxy version of the EQ-5-D and the Wong Baker FACES Pain Scale), whereas other items will be presented weekly and/or until the child is feeling better (all items of the proxy version of the EQ-5D-Y and the FLACC scale). We will ask parents to complete these questions.

Follow-up (patient health record)

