11.2 Planned recruitment rate

Our groups have successfully completed a range of trials in both children and adults with acute illnesses in primary care.

The same primary care network used in previous studies by the sponsors group will be used for recruitment, previously resulting in sample sizes of up to 8962 children.

The planned recruitment period will be 21 months. Taking into account an inclusion rate of 1 in 5 of all eligible children, we will include a total of 122 ambulatory care physicians.

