11.3 Statistical analysis plan

11.3.1 Summary of baseline data and flow of patients

Presentation of baseline characteristics of the study population and comparability of the 2 arms will be based on the following variables:

- Age (median and 25-75 percentiles)
- Gender (percentage)
- Ethnicity (percentages)
- Parental smoking status (percentage)

Differences in baseline characteristics and clinical features will be analysed through Chi-squared testing and nonparametric equality-of-medians testing to assess potential recruitment bias.

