- multicentre: six academic centres for primary care will be involved in the recruitment of 122 primary care practices
- pragmatic: criteria excluding patients from participation will be limited as well as procedures that do not reflect care as usual
- cluster: randomization occurs at the level of the primary care practice while patients are the unit of analysis
- randomized: block randomization per academic centre will be performed to assign primary care practices to either the intervention or the control arm
- controlled: the intervention will be compared with usual care
- superiority: the trial is designed to show that the intervention is superior to usual care

Randomization

In order to avoid contamination between physicians working in the same practice, randomization will happen at the level of the physician's practice.

General practice clinics and community paediatric centres will be randomized in one of the two study arms in a 1:1 ratio using a block randomization system stratified per recruiting academic centre in order to guarantee that allocation to either the usual care or the intervention arm is balanced within every region.

Stratified block randomization will be done using an electronic random numbers generator in blocks of four practices. Randomization and concealment will be centralized at the KU Leuven and conducted by a staff member not involved in data collection or delivering the intervention.

Sample size calculation

The original sample size calculation in the approved protocol version 2.0 was based on previous data from the ERNIE2 trial, assuming an overall antibiotic prescribing proportion of 26.5% in those children recruited for our trial.

The overall antibiotic proportion was found to be 18% in the first 4938 patients recruited in the ARON trial.

If we were to assume a reduction of 5.3% (proportionate to our original reduction) between the usual care group and the intervention group, using a 5% significance level (alpha 0.05), an intracluster correlation coefficient (ICC) of 0.063 (based on data from the ERNIE2 trial in the exact same population), and power of 90% (beta 0.1), this would require 63 clusters of 50 patients in both arms, resulting in 6300 children.

R code:

We used the n4props-function in the R package CRTSize, using the following command: n4props(pc = 0.2065, pe = 0.1435, m = 50, ICC = 0.063, alpha = 0.05, power=0.9, AR=1, two.tailed=TRUE, digits=3).

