Considering the pragmatic nature of this trial and in correspondence with the 10% of practices performing non-consecutive inclusion of patients (high risk of selection bias) during the ERNIE2 trial, we will perform sensitivity analyses only considering physicians who have recruited in a consecutive way. Taking into account the required sample size for this analysis of the primary study outcome, these assumptions result in a total sample size of 7000 patients.

Timing of the analysis

- Primary and secondary outcomes: April June 2024.
- Health economic study: January February 2025. This timeline is contingent upon possible delays in data availability from IMA and the efficiency of the data retrieval process.

Withdrawals

Withdrawal from the study can be initiated either by the child, their parent(s), or by the physician. As stated in the Informed Consent Form, children and their parents have the right to end their participation in the trial at any point in time and for any reason. In case a child or parent wishes to end their participation, they can do so by notifying their physician.

The treating physician can also consider a child for withdrawal from the study. However, the physician will have to discuss this option with the study coordinator and receive the consent of the latter before a final decision of withdrawal can be made.

In all instances, the reason for withdrawal will be asked for and recorded, but participants/parents are not required to share their reason for withdrawal.

Withdrawn children will not be replaced.

The patient and/or parent/legal guardian may withdraw consent at any time during the study. For the purposes of this trial, withdrawal is defined as:

The patient and/or parent/legal guardian would like to withdraw consent from study and is not willing to be followed up for the purposes of the trial at any further visits (i.e., only data collected prior to the withdrawal of consent can be used in the trial analysis).

The details of withdrawal should be clearly documented in the patient's health records and in the electronic case report form (REDCap).

Software used

REDCap version 13.7.25 (2024 Vanderbilt University).

QSR NVIVO software version 12 (QSR International Pty Ltd, Melbourne, Australia). R software version 4.2.3 (1) within R Studio (2023.12.1 Build 402) (2) using the 'glmer' function of the 'lme4' package (3) and the 'n4props' function of the 'CRTSize' package (4).

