Imputation techniques are not applicable in this dataset.

Statistical Methodology

Statistical Procedures

-

Baseline characteristics & Clinical features

Presentation of baseline characteristics of the study population and comparability of the two arms will be based on the following variables:

- Age (median and 25-75 percentiles)
- Gender (percentage)

Baseline characteristics and clinical features will be reported using frequencies and percentages, means and standard deviations or medians and interquartile ranges, and minimum / maximum, as appropriate.

Primary endpoint

For the analysis of the primary outcome, we will use a mixed-effects logistic regression analysis to account for the clustering at practice level. The child's age and study arm will be included as predefined covariates in the model. We will do this using R software using the 'glmer' function of the 'lme4' package. Results will be reported by an odds ratio (OR) with 95% confidence intervals.

Multiple imputation will be applied to deal with missing data. Ten complete datasets will be constructed and analysed. The 10 results will be combined into a final result following Rubin's rule.

We will analyse the primary endpoint according to the intention-to-treat (ITT) approach, given the pragmatic nature of our trial.

The participating physicians were asked to recruit children with an acute illness consecutively. GPs were likely to have breached the assumption of consecutive inclusions if they:

- recruited fewer than 10 patients per year;
- performed a POC CRP test on nearly all (>90%) of the included children; and/or
- included nearly exclusively children (>90%) based on a negative result on all three items of the clinical decision tree that do not need antibiotics and exclude those that might need antibiotic treatment.

Apart from the intention-to-treat analysis, a per protocol sensitivity analysis will be performed only considering physicians who have recruited children consecutively.

Secondary endpoint – Proportional measures

We will provide a descriptive analysis of the proportion of subjects with the outcome of interest for each randomization group.

A mixed-effects logistic regression model will be employed to address clustering at the practice level. The child's age and study arm will be included as predefined covariates in the model. Odds ratios, along with their corresponding 95% confidence intervals will be reported.

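### Physicians who know their arm recruit the children, and no clinical-outcome model adjusts for illness severity, so a moderate case-mix difference between arms would stay in the odds ratio

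*SAP*

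**What the plan says.** **Recruitment.** Protocol 8.1 randomises practices. Under 8.2, "children, their parents and physicians will not be masked to the practices' random allocation". Under 8.4.1, 8.4.2 and 8.5 the participating physician informs the family, judges eligibility and willingness, and seeks consent. Consecutive recruitment is asked for as an ideal. Section 11.2 sets the number of physicians thus: "Taking into account an inclusion rate of 1 in 5 of all eligible children".

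**Models.** The SAP covariate table lists study arm and age only. For the primary endpoint, a mixed-effects logistic model with practice clustering, it states: "The child's age and study arm will be included as predefined covariates in the model". The secondary and exploratory proportions and the Cox model for time to recovery use the same two terms. Only the cost model goes further, adding gender.

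**Severity data.** Protocol 8.7 puts gut feeling, temperature and dyspnoea on the eCRF, and adds: "Clinical features will be recorded before the CRP test is conducted".

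**Checks on selection.** Protocol 11.3.1 states: "Differences in baseline characteristics and clinical features will be analysed through Chi-squared testing", with the aim of detecting recruitment bias. The SAP replaces this with description, and the variables it names for comparing the arms are age and gender. Protocol 11.1.2 treats selective inclusion as a serious source of bias and lists three signs of it. The SAP turns these into a per-protocol sensitivity analysis limited to physicians judged to have recruited consecutively.

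**The concern.** Randomising practices balances practices. It does not balance the children inside them when the person choosing whom to approach already knows the arm. A practice random effect does not help, because an imbalance that runs along the arm is indistinguishable from a treatment effect in a model with arm and age alone.

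If intervention physicians enrolled milder children, or control physicians sicker ones, prescribing would differ with no effect of the algorithm. The reverse is just as possible: a physician holding a new test may bring in sicker children, and real benefit would then be hidden. The trial asks whether prescribing can be reduced safely, so the non-inferiority endpoints are exposed too. A milder intervention arm would plausibly recover sooner and re-consult less.

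**Working it through.** **1. The plan's own figure.** Inputs are in the SAP's R call: "n4props(pc = 0.2065, pe = 0.1435, m = 50, ICC = 0.063, alpha = 0.05, power=0.9, AR=1, two.tailed=TRUE, digits=3". The design effect is 1 + 49 × 0.063 = 4.087. Clusters per arm = (1.960 + 1.282)² × (0.2065 × 0.7935 + 0.1435 × 0.8565) × 4.087 / (50 × 0.063²) = 62.05, rounded up to 63. This agrees with the SAP: "this would require 63 clusters of 50 patients in both arms, resulting in 6300 children". Dividing by 0.9 gives 7000, as stated. The planned effect is 6.3 points, an odds ratio of 0.64.

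**2. How far prescribing depends on severity.** Inputs from Protocol 11.1.1: 17% of children are positive on the decision tree; among them 28% have CRP below 5 mg/L with 29% prescribed antibiotics, and 72% have CRP of 5 mg/L or more with 62% prescribed; the overall rate is 30.43%.

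- Tree-positive: 0.28 × 0.29 + 0.72 × 0.62 = 52.8%
- Tree-negative: (0.3043 − 0.17 × 0.528) / 0.83 = 25.9%
- Gap: 26.9 points, odds ratio 3.20

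**3. Shift in the arm contrast with no true effect.** Shift = gap × arm difference in tree-positive share. The documents give no figure for that difference, so it is an assumption.

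| Assumed difference | At 30.43% | Share of 7.78-point target | Scaled to 18% (× 18/30.43) | Share of stated 5.3 points | Share of coded 6.3 points |
|---|---|---|---|---|---|
| 10 points | 2.7 | 35% | 1.6 | 30% | 25% |
| 5 points | 1.3 | 17% | 0.8 | 15% | 13% |

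The 7.78-point target is 30.43% − 22.65%. The 18% is the pooled rate in the first 4938 children, not a control-arm rate.

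**4. The same on the odds-ratio scale.** Holding the odds ratio of 3.20 and setting the control rate to 20.65% gives 39.3% prescribing in tree-positive and 16.8% in tree-negative children, a gap of 22.5 points. With 6300 children, the design effect above, no true effect and 17% tree-positive in the control arm:

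| Tree-positive share, intervention arm | Spurious difference | Odds ratio | Chance of two-sided p < 0.05 |
|---|---|---|---|
| 12% | 1.1 points lower | 0.93 | about 8.5% |
| 7% | 2.2 points lower | 0.87 | about 20% |
| 29% | 2.7 points higher | 1.17 | about 25% |

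The last row is an intervention arm that enrols tree-positive children at twice the relative rate.

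**5. Whether adjustment would help.** A simulation used 126 clusters of 50, 300 runs per scenario, and a GEE logistic model in place of the planned mixed model. The age-and-arm model gave odds ratios of 0.94 (12% share) and 0.87 (7% share). Adding tree status returned both to about 1.00, with 6–7% rejections. Selection in that simulation ran through tree status, so it shows the best case for adjustment.

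**6. What the consecutive-recruiter analysis can catch.** An unselected physician has about 83% tree-negative children. One of the SAP's signs of selection starts above 90%. If it is read on tree status alone, a physician at 7% tree-positive (93% negative) is removed and one at 12% (88% negative) is kept. The sign also refers to children not needing antibiotics, and on that reading fewer are removed. In either case the primary odds ratio is unchanged.

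**The case against.** The strongest reply is that the sponsor saw this risk and acted on it. Protocol 11.1.2 makes monitoring of consecutive inclusion an aim and names an audit, monitoring visits and interviews as checks. The SAP describes clinical features, has by-arm columns in Table 1 and an inclusion flowchart, and uses the three decision-tree items to define one sign of selective recruitment. All of this stands, and part of the fix is only to make it explicit. But these measures describe or monitor, or remove physicians at the extremes; none adjusts an estimate for moderate selection. The sign based on more than 90% CRP testing is also unlikely to be met by control physicians, since practices already using the device are excluded (7.2) and controls receive no additional tools (section 9). That analysis may therefore drop physicians unequally by arm.

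Several stronger readings are tempting and are not supported:

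- **That severity differs between arms.** The documents neither report nor predict this.
- **That the 1-in-5 figure shows physicians choosing by severity.** It is a workload figure, and refusal or lack of time would explain it equally well.
- **That the three clinical items are the strongest predictors of prescribing.** Protocol 11.1.1 gives rates only for the composite tree. CRP separates more (11% against 38%, and 29% against 62%) than tree status does at fixed CRP (18 and 24 points).
- **That a 10-point difference could account for half the target.** This would set 2.7 points, which belongs to the 30.43% base rate, against 5.3 points, which belongs to 18%.
- **That the chi-squared check has a known false-alarm rate.** The documents give no intracluster correlation for baseline features, and the SAP no longer plans the test.

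It is also fair to say that a 10-point deficit from a base of 17% is a severe case.

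**Conclusion.** The concern holds as an unprotected risk in either direction. No primary, secondary or exploratory clinical-outcome model contains a measure of severity, although physicians who know the arm recruit the children and severity is recorded before the CRP result. A 5-point arm difference in tree-positive share would move the odds ratio to about 0.93 with no true effect, and a 10-point difference to about 0.87, against a planned 0.64. Selection of this size would not by itself produce the planned effect, but it could tip a borderline result or mask a real one.

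The sizes assume that the earlier trial's prescribing rates by tree status carry over to this one, and they rest on assumed imbalances. This is a cheap improvement to the SAP, not a defect that invalidates the primary analysis.

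**What to change.** Keep the primary intention-to-treat model unchanged. In the SAP, under the primary and secondary endpoints:

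1. Pre-specify a supportive analysis for the primary and the four secondary endpoints, using the same model for each. Step one adds temperature and gender. Step two adds dyspnoea and gut feeling.
2. Name temperature, dyspnoea, gut feeling, and the screening-log counts and reasons (Protocol 8.4.2) in the planned by-arm tables. Give standardised differences and no significance tests, and bring Protocol 11.3.1 into line.
3. State that the superiority result is reported alongside the severity-adjusted one.

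**Cost.** SAP wording and a two-step supportive model per endpoint, on data the protocol already collects.

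**Downside.** Dyspnoea and gut feeling are scored by unmasked physicians as part of the algorithm, so arm may influence the scores; that is why they come second. Conditional odds ratios can also shift when covariates are added, even with no imbalance, so a change between models is not in itself proof of selection. The analysis is supportive and corrects selection only in part.

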7.2 Exclusion criteria for physicians

Practices will be excluded from study participation based on the following criteria:

Currently using a POC CRP device as part of their routine care

No practices will be excluded on other grounds than the above. Age, demographics, geographic region will not be used to exclude eligible practices. This will provide us with a real-life, representative subset of ambulatory care physicians.

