
3. Non-consecutive recruitment

In the protocol, we have specified: "The participating physicians will be asked to consecutively recruit children with an acute illness over the recruitment period covering two winter seasons."

We wanted to further clarify what is meant by non-consecutive recruitment, by stating that GPs are likely to breach this assumption if:

- They recruit less than 10 patients per year
- ² CareConnect General Practitioner, Handleiding, Extra/tandwiel, Statistiek. https://careconnectmanual.corilus.be/nl/node/98. Accessed 10 January 2023.

³ Daktari gebruikersandleiding, "5.4 Geavanceerd zoeken". https://www.daktari.be/files/Daktari-handleiding.pdf. Accessed 10 January 2023.

⁴ HealthOne, Basis Handleiding. https://www.dropbox.com/s/4fwlwvr56z0wlw8/Basis%20handleiding.pdf?dl=0. Accessed 10 January 2023.

- They perform a point-of-care CRP test on nearly all (>90%) of the included children
- They deliberately only include children (>90%) that do not need antibiotics and exclude those that might need antibiotic treatment.

All of the above circumstances introduce significant selection bias and reduce the generalisability of our findings. Although we plan to perform an intention-to-treat analysis given the pragmatic nature of our trial, protocol violations caused by the inappropriate inclusion/exclusion of patients will be far more detrimental for the validity of our trial. Apart from the intention-to-treat analysis a per protocol sensitivity analysis will be performed.

The abovementioned assumptions can be tested, based on:

- the qualitative sub-study (semi-structured interviews with parents and physicians) in a selection of the recruiting practices
- the audit as described above
- monitoring visits by the clinical trial centre supporting data monitoring of the ARON trial

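### Two of the three criteria that define the consecutive-recruiter per-protocol set are unsuitable as exclusion rules: one can remove only intervention physicians, the other has no data definition

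*SAP*

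**What the plan says.** The main analysis is not in question: "We will analyse the primary endpoint according to the intention-to-treat (ITT) approach". Beside it, under Statistical Methodology, Primary endpoint, the SAP states that "a per protocol sensitivity analysis will be performed only considering physicians who have recruited children consecutively". A physician is likely to have breached consecutive recruitment if any of three criteria is met (the list is joined by and/or):

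1. "recruited fewer than 10 patients per year";
2. "performed a POC CRP test on nearly all (>90%) of the included children";
3. "included nearly exclusively children (>90%) based on a negative result on all three items of the clinical decision tree", a phrase that continues with children who do not need antibiotics and the exclusion of those who might.

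Protocol section 11.1.2 (Non-consecutive recruitment) words the third criterion without the decision tree: "They deliberately only include children (>90%) that do not need antibiotics and exclude those that might need antibiotic treatment". Neither document says which recorded variable shows that a child did not need antibiotics.

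Three further statements bear on criterion 2. Protocol 7.2 excludes practices "Currently using a POC CRP device as part of their routine care". Protocol 9 gives control physicians nothing beyond the general training. Protocol 9.2 restricts the device to use within the trial.

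**The concern.** An exclusion rule in a randomised comparison should act alike in both arms and should not depend on what the intervention changes. Criterion 2 fails the first test. It also selects on behaviour tied to the intervention: in tree-negative children the algorithm advises CRP when antibiotics are being considered, so the testing share reflects both adherence and intention to prescribe. Criterion 3 fails the second test if need is inferred from prescribing, because low prescribing is the effect the trial hopes to produce.

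This analysis carries weight. Physicians recruit children knowing their allocation, so it is the main check on selective recruitment. The sample was raised from 6300 to 7000 to support it, and Protocol 11.1.2 regards inappropriate inclusion and exclusion as a serious threat to validity. If its result differs from the intention-to-treat result, the gap may be produced by the exclusion rules. Leaving criterion 3 undefined also allows its meaning to be settled after outcomes are known.

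**Working it through.** **The plan's own figure.** Inputs from the SAP sample size section: 20.65% vs 14.35%, 50 per cluster, ICC 0.063, two-sided 5%, power 90%.

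Clusters per arm = (z0.975 + z0.90)² × [pc(1−pc) + pe(1−pe)] × [1 + (m−1)ICC] / [m(pc−pe)²] = 10.507 × (0.16386 + 0.12291) × 4.087 / (50 × 0.063²) = 62.05, so 63. Then 63 × 50 × 2 = 6300, and 6300/0.9 = 7000. Both reproduce. With 122 practices, 7000/122 is about 57 children each, so 50 and 57 are used below.

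**Criterion 2 (CRP on more than 90%).** Control physicians have no trial device, and routine users were excluded before randomisation, so the expected control exclusion rate is essentially zero. Chance is not the cause of flagging in the intervention arm. With 17% tree-positive (Protocol 11.1.1), and antibiotics considered in 30% to 50% of tree-negative children (assumption), expected testing is 0.17 + 0.83 × 0.30 = 42% to 0.17 + 0.83 × 0.50 = 58%. Fewer than 0.4% of practices with 50 children would then exceed 90%, even at ICC 0.063.

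To see the possible bias, suppose 10% of intervention practices are dropped and no control practices (assumption). The retained rate is (0.1435 − 0.10 × r)/0.90, where r is the antibiotic rate in those dropped:

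| r | Retained rate | Odds ratio vs 20.65% |
|---|---|---|
| 6.35% (8 points below arm mean) | 15.24% | 0.69 |
| 14.35% (equal) | 14.35% | 0.644 |
| 24.35% (10 points above) | 13.24% | 0.59 |

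The bias can go either way.

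**Criterion 3 judged from prescribing.** Practice rates are beta-binomial with a = p(1−ICC)/ICC and b = (1−p)(1−ICC)/ICC. A practice is dropped if more than 90% of its children receive no antibiotic, that is at most 4 prescriptions in 50 or 5 in 57. At ICC 0.063:

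| Children | Control dropped | Intervention dropped | Retained rates | Difference | Odds ratio |
|---|---|---|---|---|---|
| 50 | 15.7% | 35.1% | 23.5% vs 19.5% | 3.9 points | 0.79 |
| 57 | 17.1% | 37.7% | 23.7% vs 19.9% | 3.8 points | 0.80 |

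The planning values are 6.3 points and odds ratio 0.644. The SAP text also speaks of a 5.3-point reduction. At 20.65% vs 15.35% the exclusions are 16-17% vs 31-34%, and 5.3 points shrink to about 3.3. The imbalance does not need a high ICC: at 0.01 and 50 children it is 3.5% vs 19.3%.

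**Criterion 3 judged from tree status alone.** With 17% tree-positive, a consecutive recruiter averages 83% tree-negative. The chance of exceeding 90% (at least 46 of 50, or 52 of 57) is:

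| ICC for tree status (assumed) | 50 children | 57 children |
|---|---|---|
| 0 | 5.7% | 6.2% |
| 0.01 | 10.0% | 11.1% |
| 0.025 | 15.5% | 17.2% |
| 0.063 | 25.6% | 27.7% |

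Protocol 8.7 has the tree features recorded at baseline with no restriction by arm, so chance flagging is the same in both arms and costs power only. Losing 25.6% leaves 7000 × 0.744 = 5208 children and about 84% power, against 90% at the planned 10% loss. The SAP applies the criteria per physician and a practice may contribute two. At 25 children per physician the range is 21% to 32% for ICC 0.01 to 0.063.

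**Criterion 3 judged from both.** From Protocol 11.1.1, prescribing in tree-positive children is 0.28 × 0.29 + 0.72 × 0.62 = 52.8%. In tree-negative controls it is then (0.2065 − 0.17 × 0.528)/0.83 = 14.1%. The share tree-negative and not prescribed is 0.83 × 0.859 = 71%. Only 0.03% (no clustering) to 4.5% (ICC 0.063) of control practices with 50 children would be flagged.

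**The case against.** A reader might infer that the whole per-protocol set is biased by construction and pulls a true effect toward zero. The documents do not support that. Acting on one arm is a fault of criterion 2 alone. Tree status, taken alone, is arm-neutral. The low-recruitment criterion has neither fault. Shrinkage toward zero is shown only if need is read as prescribing, which neither document states: the protocol speaks of deliberate selection by need, and the SAP, which governs the analysis, refers to the tree.

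The 26-28% figure is also open to challenge. It borrows the prescribing ICC for tree status, for which no ICC is given. Protocol 11.1.1 says clinical outcomes tend to have lower ICCs than process outcomes and uses 0.025 for the secondary outcomes, which gives 15-17%. It also leaves out the rest of the SAP wording. Read jointly, few control practices would be flagged, although the joint share would be higher in an arm that prescribes less, so an arm difference remains possible.

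The criteria mark a likely breach rather than automatic removal, and the protocol mentions interviews in selected practices, the audit and monitoring visits as checks. But the SAP does not say how these would decide who stays in. Finally, the SAP's missing-data section already plans a sensitivity analysis that excludes only low-recruiting practices.

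These points limit the size and direction that can be claimed. They do not rescue criterion 2, and they do not supply a definition for criterion 3.

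**Conclusion.** The point holds for two of the three criteria. Criterion 2 makes the per-protocol set depend on post-randomisation behaviour in one arm, so the comparison is no longer randomised. This follows from the documents without any assumed figure, but the direction and size of the bias are unknown (the odds ratios of 0.59 to 0.69 are illustrations). Criterion 3 is undefined, and its consequences depend on the reading: a material arm imbalance and attenuation from 6.3 to 3.8-3.9 points if judged from prescribing, or an arm-neutral loss of 6% to 28% of consecutive recruiters if judged from tree status alone. Those ranges rest on 50 to 57 children per practice, a beta-binomial model and, for tree status, an assumed ICC. The intention-to-treat result is untouched. What is compromised is the reading of a named sensitivity analysis for which the sample was enlarged.

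**What to change.** In the SAP, do not exclude physicians from this analysis by the CRP criterion or by any criterion based on prescribing or need for antibiotics. Define the consecutive-recruiter set by the rule of fewer than 10 patients per year, already prespecified in the SAP's missing-data section. The SAP puts the loss from that rule at about 10% of practices (Protocol 11.3.4 says about 5%), so it fits the allowance behind 7000. Report the CRP-testing and tree-negative shares descriptively by arm, and the numbers of practices and physicians excluded by arm.

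This costs SAP wording only and needs no new data. The downside is that some selectively recruiting practices stay in the set. A criterion on the ratio of included to eligible children, with one cut-off for both arms, is optional. It should be used only if the screening log proves complete enough in both arms. That is not assured: the log holds reasons only where given, and the audit queries shown count consultations by age rather than eligible acute illness.
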